#### **Telephone Call 6 (8 [+2] days after Visit 6)**

Refer to steps in Telephone Call 1.

#### **Visit 7 (30 [+21] days after Visit 6; 16 to 19 months of age ): Collection of Safety Information, Blood Sample and Study Termination**

- 1) Collect and review the diary card (DC6) with the parent / guardian, including any AEs, medications, or therapy that occurred since vaccination. If an SAE, including an AESI, has occurred, follow the instructions in [Section 10](#) for reporting it.
- 2) Review temporary contraindications for blood sampling. Ensure the subject has not had any antibiotics within the previous 72 hours (3 days).
- 3) Collect 5 mL of blood (BL4) (see [Section 7](#) for detailed instructions regarding the handling of blood samples).
- 4) Give the parent / guardian a memory aid to record SAE and MAAEs from Visit 7 until the 6-month follow-up phone call.
- 5) Remind the parent / guardian / to notify the site in case of an SAE.
- 6) Complete the trial termination record.

#### **Safety Follow-up Telephone Call 7 (180 [+30] days after Visit 6): Collection of SAEs (including AESIs) and MAAEs**

- 1) Ask the parent / guardian if the subject has experienced any SAE/MAAE since the last study visit. If an SAE, including an AESI, has occurred, follow the instructions in [Section 10](#) for reporting it.
- 2) Complete the relevant CRFs for this visit.

This call must be made by a qualified person, such as a physician or qualified study nurse.

A follow-up visit outside the scope of this study protocol can be arranged depending on the information recorded during the phone calls.

***SAEs and AEs That Are Related to Vaccination or That Led to Discontinuation:***

***Follow-up of subjects with Related AEs or with AEs That Led to Study/Vaccination Discontinuation:***

A subject who experiences an AE (whether serious or non-serious) during the study must be followed until the condition resolves, becomes stable, or becomes chronic (even after the end of the subject's participation in the study) if *either* of the following is true:

The AE is considered by the Investigator to be related to the product administered.

The AE caused the discontinuation of the subject from the study or from vaccination.

**5.1.5 Planned Study Calendar**

The following dates are approximate. The actual dates may differ as, for example, the study will not start until all the appropriate regulatory and ethical approvals have been obtained.

Planned study period - FVFS (first visit, first subject) to LCLS (last contact, last subject): 25 April 2018 to 29 August 2023

Planned inclusion period - FVFS to FVLS (first visit, last subject): 25 April 2018 to 30 September 2021

Planned end of study: 29 August 2023

Planned date of final clinical study report: 26 February 2024

**5.1.6 Early Safety Data Review**

No Early Safety Data Review (i.e., no early safety review[s] of preliminary safety data occurring at pre-determined milestones defined in the protocol, with pause in enrollment) is planned for this trial as MenACYW conjugate vaccine has been previously administered to infants, toddlers, and adults with an acceptable safety profile and no safety concerns have been identified in the clinical trials completed so far. There will be an internal team at the level of the Sponsor (Safety Management Team, [SMT]), which will review the data being generated from all the ongoing studies with MenACYW conjugate vaccine at regular intervals for any new safety signals or safety concerns. The SMT is empowered to recommend a pause in both recruitment and / or further vaccination while it investigates any potential signal or concern.

This trial will not include an early review of safety data. However, it may be interrupted at any time if new data about the investigational product become available, and/or on advice of the Sponsor, the Independent Ethics Committees (IECs) / Institutional Review Boards (IRBs), or the governing regulatory authorities in the US where the trial is taking place.

If the trial is prematurely terminated or suspended, the Sponsor will promptly inform the Investigators, the IECs/IRBs, and the regulatory authorities of the reason for termination or suspension. If the trial is prematurely terminated for any reason, the Investigator will promptly inform the subjects' parents / guardians and should assure appropriate therapy and follow-up.

## 5.2 Enrollment and Retention of Trial Population

### 5.2.1 Recruitment Procedures

Each site will be responsible for devising a recruitment plan for enrolling eligible subjects. Advertisements and other recruitment aids will be approved by the Sponsor and the site's IRB/IEC prior to use by the clinical site.

### 5.2.2 Informed Consent Procedures

Informed consent is the process by which a subject and / or a parent / guardian voluntarily confirms his or her willingness to participate / allow the child to participate in a particular study. Informed consent must be obtained before any study procedures are performed. The process is documented by means of a written, signed, and dated ICF.

In accordance with GCP, prior to signing and dating the consent form, the parent / guardian must be informed by appropriate study personnel about all aspects of the study that are relevant to making the decision to participate, and must have sufficient time and opportunity to ask any questions.

The actual ICF used at each center may differ, depending on local regulations and IEC / IRB requirements. However, all versions must contain the standard information found in the sample ICF provided by the Sponsor. Any change to the content of the ICF must be approved by the Sponsor and the IEC / IRB prior to the form being used.

If new information becomes available that may be relevant to the parent's / guardian's willingness to continue participation in the study, this will be communicated to him / her in a timely manner. Such information will be provided via a revised ICF or an addendum to the original ICF.

ICFs will be provided in duplicate, or a photocopy of the signed consent will be made. The original will be kept by the Investigator, and the copy will be kept by the subject's parent / guardian.

Documentation of the consent process should be recorded in the source documents.

### 5.2.3 Screening Criteria

There are no screening criteria other than the inclusion and exclusion criteria.

### 5.2.4 Inclusion Criteria

An individual must fulfill *all* of the following criteria in order to be eligible for trial enrollment:

- 1) Aged  $\geq 42$  to  $\leq 89$  days on the day of the first study visit.
- 2) Healthy infants as determined by medical history, physical examination, and judgment of the investigator
- 3) Informed consent form has been signed and dated by the parent(s) or guardian, and an independent witness, if required by local regulations
- 4) Subject and parent/guardian are able to attend all scheduled visits and to comply with all trial procedures.

- 5) Infants who received the first dose of hepatitis B vaccine at least 28 days before the first study visit

### 5.2.5 Exclusion Criteria

An individual fulfilling *any* of the following criteria is to be excluded from trial enrollment:

- 1) Participation at the time of study enrollment or in the 4 weeks preceding the first trial vaccination or planned participation during the present trial period in another clinical trial investigating a vaccine, drug, medical device, or medical procedure
- 2) Receipt of any vaccine in the 4 weeks preceding the first trial vaccination or planned receipt of any vaccine in the 4 weeks before and/or following any trial vaccination except for influenza vaccination, which may be received at a gap of at least 2 weeks before or 2 weeks after any study vaccination. This exception includes monovalent pandemic influenza vaccines and multivalent influenza vaccines
- 3) Previous vaccination against meningococcal disease with either the trial vaccine or another vaccine (i.e., mono- or polyvalent, PS, or conjugate meningococcal vaccine containing serogroups A, C, Y, or W; or meningococcal B serogroup-containing vaccine).
- 4) Previous vaccination against diphtheria, tetanus, pertussis, poliomyelitis, hepatitis A, measles, mumps, rubella, varicella; and of *Haemophilus influenzae* type b, *Streptococcus pneumoniae*, and /or rotavirus infection or disease
- 5) Receipt of more than 1 previous dose of hepatitis B vaccine
- 6) Receipt of immune globulins, blood, or blood-derived products since birth
- 7) Known or suspected congenital or acquired immunodeficiency; or receipt of immunosuppressive therapy, such as anti-cancer chemotherapy or radiation therapy; or long-term systemic corticosteroid therapy (prednisone or equivalent for more than 2 consecutive weeks) since birth
- 8) Family history of congenital or hereditary immunodeficiency, until the immune competence of the potential vaccine recipient is demonstrated
- 9) Individuals with blood dyscrasias, leukemia, lymphoma of any type, or other malignant neoplasms affecting the bone marrow or lymphatic systems
- 10) Individuals with active tuberculosis
- 11) History of any *Neisseria meningitidis* infection, confirmed either clinically, serologically, or microbiologically
- 12) History of diphtheria, tetanus, pertussis, poliomyelitis, hepatitis B, hepatitis A, measles, mumps, rubella, varicella; and of *Haemophilus influenzae* type b, *Streptococcus pneumoniae*, and /or rotavirus infection or disease
- 13) At high risk for meningococcal infection during the trial (specifically, but not limited to, subjects with persistent complement deficiency, with anatomic or functional asplenia, or subjects travelling to countries with high endemic or epidemic disease)
- 14) History of intussusception

- 15) History of any neurologic disorders, including any seizures and progressive neurologic disorders
- 16) History of Guillain-Barré syndrome
- 17) Known systemic hypersensitivity to any of the vaccine components or to latex, or history of a life-threatening reaction to the vaccine(s) used in the trial or to a vaccine containing any of the same substances, including neomycin, gelatin, and yeasta
- 18) Verbal report of thrombocytopenia contraindicating intramuscular vaccination in the investigator's opinion
- 19) Bleeding disorder, or receipt of anticoagulants in the 3 weeks preceding inclusion, contraindicating intramuscular vaccination in the investigator's opinion
- 20) Receipt of oral or injectable antibiotic therapy within 72 hours prior to the first blood draw
- 21) Chronic illness (including, but not limited to, cardiac disorders, congenital heart disease, chronic lung disease, renal disorders, auto-immune disorders, diabetes, psychomotor diseases, and known congenital or genetic diseases) that, in the opinion of the investigator, is at a stage where it might interfere with trial conduct or completion
- 22) Any condition which, in the opinion of the investigator, might interfere with the evaluation of the study objectives
- 23) Moderate or severe acute illness/infection (according to investigator judgment) on the day of vaccination or febrile illness (temperature  $\geq 38.0^{\circ}\text{C}$  [ $\geq 100.4^{\circ}\text{F}$ ]). A prospective subject should not be included in the study until the condition has resolved or the febrile event has subsided
- 24) Identified as a natural or adopted child of the investigator or employee with direct involvement in the proposed study

If the subject has a primary physician who is not the Investigator, the site must contact the primary physician to inform him / her of the subject's participation in the study. In addition, the site should ask this primary physician to verify exclusion criteria relating to previous therapies, such as receipt of blood products or previous vaccines.

### 5.2.6 Medical History

Prior to enrollment, subjects will be assessed for pre-existing conditions and illnesses, both past and ongoing. Any such conditions will be documented in the source document. Significant medical history (reported as diagnosis) including conditions for which the subject is or has been followed by a physician or conditions that could resume during the course of the study or lead to an SAE or to a repetitive outpatient care will be collected in the CRB. The significant medical history section of the CRB contains a core list of body systems and disorders that could be used to prompt comprehensive reporting, as well as space for the reporting of specific conditions and illnesses.

---

a The components of all study vaccines are listed in Section 6.1.1 and in the Investigator's Brochure

For each condition, the data collected will be limited to:

- Diagnosis (this is preferable to reporting signs and symptoms)
- Presence or absence of the condition at enrollment

The reporting of signs and symptoms in lieu of a diagnosis is strongly discouraged.

Dates, medications, and body systems are not to be recorded, and the information collected will not be coded. Its purpose is to assist in the later interpretation of safety data collected during the trial.

In addition, maternal immunization history will be collected in the CRB as follows:

- Tdap vaccination received during pregnancy with the subject enrolled in the study and date of vaccination
- Any meningococcal vaccination received at any time (name or type of meningococcal vaccine, i.e. Menactra, meningococcal ACWY conjugate vaccine, meningococcal B vaccine, etc.) and date of vaccination

The information collected will not be coded. This information will further assist with the interpretation of data collected during the trial.

## 5.2.7 Contraindications for Subsequent Vaccinations

### 5.2.7.1 Temporary Contraindications

Should a subject experience one of the conditions listed below, the Investigator will postpone further vaccination until the condition is resolved. Postponement must still be within the timeframe for vaccination indicated in the Table of Study Procedures.

- Febrile illness (temperature  $\geq 38.0^{\circ}\text{C}$  [ $\geq 100.4^{\circ}\text{F}$ ]) or moderate or severe acute illness / infection on the day of vaccination, according to Investigator judgment.
- Receipt of any vaccine (other than the study vaccines) in the 4 weeks preceding the first study vaccination or planned receipt of any vaccine in the 4 weeks before or following any study vaccination except for influenza vaccination, which may be received at least 2 weeks before or 2 weeks after any study vaccination. This exception includes monovalent pandemic influenza vaccines and multivalent influenza vaccines.

The following is a temporary contraindication to blood draws:

- Receipt of oral or injected antibiotic therapy within the 72 hours (3 days) prior to a study blood draw. *Note:* If following the first visit, a subject receives oral or injectable antibiotic therapy within 3 days prior to the next blood draw, the investigator will postpone that blood draw until it has been 3 days since the subject last received oral or injectable antibiotic therapy. Postponement must still be within the timeframe for blood draw. If postponement would result in the sample collection falling outside of this timeframe, the blood sample should be collected without postponement, and it should be documented appropriately that the sample was taken less than 3 days after stopping antibiotic treatment.

### 5.2.7.2 Definitive Contraindications

Should a subject experience an anaphylactic or other significant allergic reaction to the previous dose of vaccine(s), the Investigator will discontinue vaccination(s).

The following AEs constitute absolute contraindications to subsequent vaccination with any of the study vaccines. If a subject should experience any of these events during the study, that subject is not to receive any additional study vaccines but should continue in the study and be followed up for safety only as per protocol.

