**Pentacel®: DTaP-IPV//Hib vaccine**

- 4) Severe allergic reaction (e.g., anaphylaxis) after a previous dose of Pentacel®, any ingredient of Pentacel®, or any other diphtheria toxoid, tetanus toxoid, pertussis-containing vaccine, inactivated poliovirus vaccine or *H. influenzae* type b vaccine.
- 5) Encephalopathy within 7 days of a previous pertussis-containing vaccine with no other identifiable cause.
- 6) Progressive neurologic disorder including infantile spasms, uncontrolled epilepsy, or progressive encephalopathy until a treatment regimen has been established and the condition has stabilized.

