**RotaTeq®: rotavirus vaccine**

- 9) Demonstrated history of hypersensitivity to the rotavirus vaccine or any component of the vaccine.
- 10) Episode of intussusception.
- 11) History of severe combined immunodeficiency (SCID).

**M-M-R® II:** measles, mumps, and rubella vaccine

- 12) Hypersensitivity to any component of the vaccine, including gelatin.
- 13) Anaphylactic or anaphylactoid reactions to neomycin
- 14) Febrile respiratory illness or other active febrile infection.
- 15) Patients receiving immunosuppressive therapy. This contraindication does not apply to patients who are receiving corticosteroids as replacement therapy, e.g., for Addison's disease.
- 16) Individuals with blood dyscrasias, leukemia, lymphomas of any type, or other malignant neoplasms affecting the bone marrow or lymphatic systems.
- 17) Primary and acquired immunodeficiency states, including patients who are immunosuppressed in association with acquired immune deficiency syndrome (AIDS) or other clinical manifestations of infection with human immunodeficiency viruses; cellular immune deficiencies; and hypogammaglobulinemic and dysgammaglobulinemic states.
- 18) Individuals with a family history of congenital or hereditary immunodeficiency, until the immune competence of the potential vaccine recipient is demonstrated.

**VARIVAX®:** varicella vaccine

- 19) History of severe allergic reaction to any component of the vaccine (including neomycin and gelatin) or to a previous dose of varicella vaccine.
- 20) History of primary or acquired immunodeficiency states, leukemia, lymphoma or other malignant neoplasms affecting the bone marrow or lymphatic system, AIDS, or other clinical manifestations of infection with human immunodeficiency virus (HIV).
- 21) Individuals receiving immunosuppressive therapy, including individuals receiving immunosuppressive doses of corticosteroids.
- 22) Any febrile illness or active infection, including active, untreated tuberculosis.

**HAVRIX®:** hepatitis A vaccine

- 23) Severe allergic reaction (e.g., anaphylaxis) after a previous dose of any hepatitis A-containing vaccine, or to any component of HAVRIX®, including neomycin.

In the event of a local or national immunization program with a pandemic influenza vaccine, subjects who receive pandemic influenza vaccine at any time during the study will not be withdrawn from the study.

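### Protocol 5.2.7.2 makes febrile illness and active infection absolute bars to all further study vaccine, while 5.2.7.1 and every vaccination visit say to postpone for fever

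*Protocol*

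**What the plan says.** Protocol 5.2.7.2 opens its numbered list with "The following AEs constitute absolute contraindications to subsequent vaccination with any of the study vaccines". The consequence for a child who has a listed event during the study is "that subject is not to receive any additional study vaccines but should continue in the study and be followed up for safety only". The footnote to Protocol 12.2.1.3 defines a study vaccine to include the investigational, control and routine vaccines.

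The list is grouped under vaccine names. Four entries matter here:

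- Item 14 (M-M-R II): "Febrile respiratory illness or other active febrile infection".
- Item 22 (VARIVAX): "Any febrile illness or active infection, including active, untreated tuberculosis".
- Item 6 (Pentacel), progressive neurologic disorder, which applies "until a treatment regimen has been established and the condition has stabilized".
- Item 18 (M-M-R II), family history of immunodeficiency, which applies "until the immune competence of the potential vaccine recipient is demonstrated".

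Protocol 5.2.7.1 takes the other course: "Should a subject experience one of the conditions listed below, the Investigator will postpone further vaccination until the condition is resolved". The conditions it lists include febrile illness at 38.0°C or above, or "moderate or severe acute illness / infection on the day of vaccination, according to Investigator judgment". Postponement must stay within the visit window. The visit procedures in 5.1.4.1 and 5.1.4.2 repeat the postponement rule for a temperature of 38°C or more at every vaccination visit.

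**The concern.** Fever is both a reason to wait and a reason to stop for good. The lead-in to 5.2.7.2 puts no severity or time limit on items 14 and 22 and extends them to every study vaccine. A site that applies it literally would end all vaccination in a child with an ordinary febrile infection. A site that postpones would be vaccinating against a rule labelled absolute.

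Two things are at stake: whether an infant receives the remaining meningococcal and routine doses in the study, and whether the child stays in the per-protocol sets on which immunogenicity is primarily analysed.

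**Working it through.** **Comparing the rules**

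| Situation | 5.2.7.1 and visit steps | 5.2.7.2 as worded |
|---|---|---|
| Febrile illness on a vaccination day | Postpone, then vaccinate | No further study vaccine |
| Moderate or severe infection on the day, no fever | Postpone (5.2.7.1 only) | No further study vaccine (item 22) |
| Mild infection without fever | Not covered | No further study vaccine (item 22) |
| Febrile illness between visits, resolved by the next | Not covered | No further study vaccine (item 22) |

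The first two rows conflict directly. In the last two, item 22 reaches further than the postponement rule. Nothing in the protocol or SAP ranks the two sections, and nothing confines items 14 and 22 to their own vaccines or to the duration of the illness.

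**Effect on the analysis sets**

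- PPAS1 (Protocol 12.2.3.1) drops a child whose infant vaccine course is incomplete. A child barred only after Visit 3 is unaffected.
- PPAS3 (Protocol 12.2.3.3) requires the schedule through the 12-month vaccinations for Subgroups 1a and 2a, and correct concomitant vaccines in the second year. A child in these subgroups barred only after Visit 5 is unaffected.
- If items 14 and 22 reach only M-M-R II and VARIVAX, both first given at Visit 5, PPAS1 is untouched and only PPAS3 can lose children.

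**Illustrative power**

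The plan's inputs (Protocol Table 12.2) are 770/385 evaluable for Primary 1, with response 80% for A and 90% for C, Y and W. For Primary 2 they are 1155/577, with 70% for A and 80% for C, Y and W. The margin δ is 10%. With equal true rates p and one-sided 2.5% error, Farrington-Manning power is

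Φ[(δ − 1.96·s0)/s1], where s1 = √{p(1−p)(1/n1 + 1/n2)} and s0 uses the two rates fitted under a true difference of −δ.

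Primary 1, serogroup A: the fitted rates are 0.757 and 0.857, so s0 = √(0.757×0.243/770 + 0.857×0.143/385) = 0.0236. Also s1 = √{0.16×(1/770 + 1/385)} = 0.0250. Power = Φ[(0.1 − 0.0463)/0.0250] = Φ(2.15) = 98.4%, as planned. The other tests give 99.98% (Primary 1 C, Y, W), 99.16% (Primary 2 A) and 99.89% (Primary 2 C, Y, W). The product of all eight is 0.9843 × 0.9998³ × 0.9916 × 0.9989³ = 97.2%, the protocol's overall figure.

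Let f be the share of otherwise evaluable children who are barred. It is an assumption, equal in both arms and on top of the planned 34.1% non-evaluable. Scale the evaluable numbers by (1 − f):

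| f | Overall power, all vaccines stopped (both objectives scaled) | Overall power, M-M-R II/VARIVAX only (Primary 1 scaled) |
|---|---|---|
| 0% | 97.2% | 97.2% |
| 5% | 96.3% | 96.7% |
| 10% | 95.0% | 96.1% |
| 20% | 91.3% | 94.2% |
| 30% | 84.8% | 91.0% |
| 40% | 73.9% | 85.6% |

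Example at f = 20% (616/308 and 924/462): 0.9582 × 0.9984³ × 0.9737 × 0.9944³ = 91.3%. Leaving Primary 2 at its planned size gives 0.9582 × 0.9984³ × 0.9916 × 0.9989³ = 94.2%. Rounding of half-subjects can move the 10% and 30% rows by 0.1 point.

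Secondary hypothesis 2 (PRP after dose 3, 5% margin, planned 94.3%) falls to 88.9% at f = 20% and 79.0% at f = 40% in the all-vaccine case. It stays at 94.3% on the narrower reading.

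**The case against.** The procedures that staff follow step by step already choose. All vaccination visits postpone for a temperature of 38°C or more, including the Visit 5 scripts where M-M-R II and VARIVAX are given. The vaccine headings, the present-tense sense of an active infection and the time limits written into items 6 and 18 all suggest vaccine-specific, temporary contraindications under a badly worded lead-in. On that view few or no children would be barred, and f values of 20% to 40% have no support.

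Most of this stands, and it limits the size of the problem. It does not remove the conflict, because the lead-in says the opposite of the inferred intent. Even with the items confined to their own vaccines, a child febrile at Visit 5 is definitively barred from M-M-R II and VARIVAX in one section and postponed for them in another.

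A reader might infer three stronger points that the documents do not support:

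- **Every febrile child leaves both PPAS1 and PPAS3.** Loss depends on when the illness occurs.
- **Post-vaccination fever would remove children unequally by arm.** Fever is a solicited reaction (Protocol Table 9.2), but no passage indicates a difference in fever between arms or tells sites to treat a solicited reaction as a barring illness.
- **An ordinary fever would be coded as termination for an adverse event under 5.2.10.** That section classifies children who discontinue the study, whereas 5.2.7.2 keeps the barred child in it.

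**Conclusion.** The inconsistency is real. Followed as written, 5.2.7.2 permanently stops all study vaccines for events that 5.2.7.1 and the visit steps treat as a delay, and item 22 also catches mild afebrile infection and illness between visits.

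The practical effect is probably small because the visit scripts point to postponement. The documents give no rate of febrile illness and no measure of how sites read the list, so the number of children affected cannot be derived. The power figures are conditional on an assumed f, equal loss in both arms, no overlap with the planned non-evaluable share, and multiplication of the eight tests as in the plan. The all-vaccine column is a worst case and also applies one f to both objectives, although loss before dose 3 would be smaller than loss before dose 4. If every site postpones, f = 0 and the planned 97.2% is unchanged.

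The case for correcting the text does not rest on f: the protocol should not contain an absolute rule that works only if sites disregard it.

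**What to change.** 1. Move items 14 and 22 from 5.2.7.2 to 5.2.7.1 as temporary contraindications, keeping active untreated tuberculosis as definitive if that is intended.
2. State that items 6 and 18 cease to apply once their own conditions are met.
3. Replace the blanket reference to all study vaccines in the 5.2.7.2 lead-in with a statement of which events stop only the named vaccine and which stop every study vaccine.

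The cost is a wording change in 5.2.7 and a clarification letter to sites. It needs no new data, visits or children.
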